The main hypothesis is that I-EWS will be non-inferior to the existing NEWS algorithm regarding 30-day mortality, but the introduction of clinical assessment results in fewer I-EWS scores per patient per day than with NEWS.

Method

The study is a prospective, cluster randomized, cross-over, non-inferiority study. The participating eight hospitals are randomly assigned to six and a half months with either I-EWS or the existing EWS track and trigger system. Computer generated numbers are used to randomize the hospitals to either the intervention or control arm of the study. A single cross-over will take place resulting in a total study period of 13 months. I-EWS is only available at hospitals assigned to I-EWS (Grey areas in the figure below). All EWS scores and subsequent actions are documented in real time. Each period will start with 14 days of implementation, and before cross-over patients will be followed by an observation period of 30 days (indicated by shaded areas below).

Hospital	1 period: 6 ½ months	2. period: 6 ½ months
Herlev & Gentofte Hospital (2 units)	Cluster 1	Cluster 1
Amager og Hvidovre Hospital (2 unit)	Cluster 2	Cluster 2
Nordsjællands Hospital (2 units)	Cluster 3	Cluster 3
Bispebjerg Hospital (1 unit)	Cluster 4	Cluster 4
Glostrup Hospital (1 unit)	Cluster 5	Cluster 5
Sjællands Universitetshospital (2 units)	Cluster 6	Cluster 6
Slagelse Hospital (1 unit)	Cluster 7	Cluster 7
Holbæk Hospital (1 unit)	Cluster 8	Cluster 8

Intervention: Prior to project start ambassadors from all the participating wards will receive 2 hours of education depending on which EWS their hospital is randomized to use. Hospitals randomized to use I-EWS will receive an introduction course and hospitals using EWS will receive a brush-up course. Subsequently, they will be responsible for teaching at their respective wards. I-EWS, like the current EWS, will apply systematic observation, where patients continue to be evaluated according to vital signs and assigned a score of 0-20. The innovation in I-EWS is that SP systematically calls for staff to reassess the assigned score after they have entered the patient's vital signs. Afterwards it is possible to adjust the score by a maximum of +6 or -4. Nursing staff reevaluate when vital signs and clinical assessment are compared, whether the patient is in the correct observation range, and if the clinical actions defined for this range is relevant.

Ethics

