The study is designed as a non-inferiority study to show that I-EWS is not inferior to the existing EWS algorithm with a non-inferiority margin (Δ) of 0.5% regarding 30-day all-cause mortality. The participating hospitals will admit 189,000 individual patients within one-year, individual sizes (admissions) are described on p.12. The sample size is based on the following assumptions: I) within a the inclusion period of ten months, the participating hospitals are expected to admit 150,000 individual patients II) mean all-cause mortality is 2.9% with variations as described on p. 11, III) a variation in mortality of 25% over the course of the year. The non-inferiority margin is set at 0.5%, and if the intervention has an effect of 0, the study has above 90% power to confirm noninferiority. In a previous cohort of 103,733 patients the mean (SD) number of scores per patient per day was 2.3 (2.0) and 15.4% of patients had one NEWS score of ≥ 6 . With the expected

inclusion, we will be able to detect a difference of 0.04 in mean number of scores and a difference of 0.6% in the number of patients with one NEWS \geq 6 with a power > 90%.

Study end

The follow-up for all patients ends after at total study period of 13 Months and is expected to end at the October 31, 2019.

Statistical plan for main outcome paper

Statistical analyses will be performed using SAS and R. Reporting of results will be in accordance with the CONSORT criteria with extension to cluster randomised trials. Analyses will be done using R. P < 0.05 will be considered statistically significant.

Consort diagram

A modified CONSORT trial profile will be used to describe patient flow and total number patients in each group and at each cluster. All patients not included in analysis will be explained.

Baseline description of groups:

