Table of summary statistics for patients and at hospital or cluster level for each group (intervention or control) will be presented with baseline variables (Number of patients, number of admissions, age, sex, Charlson Comorbidity index, hospital characteristics) Continuous variables will be summarized with: n (based on non-missing sample size), mean, standard deviation, median, interquartile range, number of missing values. Categorical variables will be reported as frequency and percentages (based on non-missing sample size) and number of missing values. Continuous and ordinal variables will be tested by Wilcoxon analysis or t-tests as appropriate for differences between groups. Categorical variables will be tested with chi-square.

Primary outcome analysis

The primary outcomes will be an **analysis of all-cause mortality and NEWS/I-EWS scores per patient per day between the intervention and control group**. Patients will be followed as one cohort and data will be analysed as randomized and in accordance with the intention-to-treat principle.

Inclusion: Patients will be included at the first admission at the participating hospitals in the study period (index admission) and will remain in this group (intervention/control) for follow-up of 30 days. Admission is defined as a contact to a hospital with a duration of more than 24 hours. All subsequent admissions (readmission) will be ignored. Any patient lost to follow-up will be censored at the last time known to be alive.

The main analysis of the primary outcome for motality will be done using logistic regression that accounts for clustering with adjustment for hospital ID, age, and sex. Intraclass correlation

coefficient with 95% confidence intervals will be reported. Results will be presented at the individual patient level. Assessment of cluster-level differences will be performed. NEWS/I-EWS scores per patient per day will be compared using linear regressions.

Each period will start with 14 days of implementation, and before cross-over patients will be followed by an observation period of 30 days Periods of implementation and observation will be censored in the analyses (patients admitted in these periods will not be included in the analyses). Cumulative incidence plots (1-survival) will be calculated using the Kaplan-Meier method and presented.

Sensitivity analyses of the primary endpoint

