In addition to the ITT analysis, a per-protocol analysis will be performed. In this analysis, interventional patients with missing or incomplete (missing a I-EWS modification in more than 1/3 of the total number of measurements) I-EWS measurement will be excluded. Finally, a sensitivity analysis will be performed, where patients that are transferred between hospitals will be excluded. Sensitivity analyses will be performed for the last three months of each intervention period and excluding departments where I-EWS protocol was not followed.

Subgroup analyses of primary endpoint

The primary outcomes will be calculated for the following subgroups, including a test for interactions: Age (\leq 39 years, 40 to 69 years, \geq 70 years), admissions at defined cluster, and according to the primary discharge diagnosis; cardiovascular disease, infections, pulmonary disease neurological disease, cancer and surgery done during admission. Results will be presented graphically using a forest plot.

Secondary endpoints

Secondary endpoints regarding mortality will be analysed using the same analysis as the primary endpoint. Length of hospital stay between groups will be compared by linear regression following the same adjustment principles as for the primary outcome.

Additional measurements

The frequency of changes in I-EWS that led to an escalation or de-escalation in the escalation protocol will be reported. Changes in NEWS due to CROS values and changes in I-EWS due to clinical assessment will be compared using Poisson regression models.

Handling of missing data

The primary outcome analysis should be subject to no or little missing data as it is based on Danish register data. Patients lost to follow-up (tourists) will be censored at the last registration.

Handling of diagnoses for outcome and subgroups

Diagnoses obtained from the National Patient Registry are coded with the ICD-10 system. The original chapters will be used to group patients according to diagnoses. The primary diagnosis will be used when constructing. The following will define the subgroups: **Cancer:** Chapter II: Neoplasms (C00-C97 + D37-D48). **Cardiovascular disease:** Chapter IX: Diseases of the circulatory system (I09-I52 + I70-I89)

Pulmonary disease: Chapter X: (DJ00-DJ99)

Infections: Chapter I: (A00-B99 + J00-J22 + N10-N11+ N30-N31 + G00-G09)

Neurological disease: Chapter VI: Diseases of the nervous system (G09-G47 + I60-I69)

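### The primary mortality analysis is not linked to the 0.5-point non-inferiority margin: no effect measure, interval or decision rule is stated

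*SAP*

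**What the plan says.** - Hypothesis: "The main hypothesis is that I-EWS will be non-inferior to the existing NEWS algorithm regarding 30-day mortality".
- Sample size calculation: the study has a "non-inferiority margin (Δ) of 0.5% regarding 30-day all-cause mortality", and then "The non-inferiority margin is set at 0.5%, and if the intervention has an effect of 0, the study has above 90% power". The same paragraph gives a detectable "a difference of 0.6% in the number of patients with one NEWS" of 6 or more.
- Statistical plan for main outcome paper: "P < 0.05 will be considered statistically significant". This is a general rule, with no sidedness and no separate criterion for non-inferiority.
- Primary outcome analysis: "The main analysis of the primary outcome for motality will be done using logistic regression that accounts for clustering", with hospital, age and sex as covariates, by intention to treat. The one interval named belongs to the intraclass correlation: "coefficient with 95% confidence intervals will be reported".
- Secondary endpoints: "Secondary endpoints regarding mortality will be analysed using the same analysis as the primary endpoint".

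Neither the margin nor the word non-inferiority appears after the sample size section. The per-protocol and other sensitivity analyses do not mention the margin either.

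**The concern.** A non-inferiority conclusion needs three things fixed in advance: the scale on which the treatments are compared, the interval (or equivalent test) for that comparison, and the rule that sets it against the margin. The SAP gives a margin and a model but none of these three. The model's coefficient is a log odds ratio, while the margin is a difference in risk, so the two cannot be compared without a conversion that the SAP does not specify.

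At stake is the main conclusion on a mortality endpoint. The conversion, the interval level and the way the general P < 0.05 rule bears on the primary endpoint would all be left open until after the data are seen. Under that rule, a significant difference could be read as failure, or a non-significant one as success. Neither reading is a test of the margin.

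**Working it through.** **Inputs.** Margin 0.5%, mortality 2.9%, 150,000 patients and true effect 0 (Sample size calculation). Allocation is 1:1, so about 75,000 per arm. Lowest and highest hospital mortality, as printed in the table at the end of the SAP: 2.42% and 3.77%. The SAP gives no intraclass correlation or design effect; any design effect below is an assumption.

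**1. The plan's power figure.** Without clustering, SE = sqrt(2 × 0.029 × 0.971 / 75,000) = 0.000867, or 0.0867 points. At one-sided 2.5%:
- Absolute margin: Φ(0.005/0.000867 − 1.96) = 99.99%. This agrees with the stated figure of above 90%, which holds up to a design effect of (0.5 / (3.2415 × 0.0867))² ≈ 3.17.
- Relative margin (0.5% of 2.9% = 0.0145 points): Φ(0.000145/0.000867 − 1.96) = 3.7%. This does not agree.

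**2. How the same paragraph uses the percent sign.** For the proportion with a score of 6 or more, SE = sqrt(2 × 0.154 × 0.846 / 75,000) = 0.001864. The difference detectable with 90% power is 3.2415 × 0.001864 = 0.604 absolute points, which matches the printed 0.6%. Together, steps 1 and 2 support reading the margin as 0.5 absolute percentage points.

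**3. The margin on the model's scale.** OR = odds(p + 0.005) / odds(p):

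| Reference mortality | OR equal to 0.5 points | Excess allowed if OR is held at 1.178 |
|---|---|---|
| 2.42% | 1.213 | 0.42 points |
| 2.9% | 1.178 | 0.50 points |
| 3.77% | 1.139 | 0.64 points |

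The odds ratio that corresponds to the margin depends on the reference rate, and the SAP fixes none.

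**4. P < 0.05 against the margin.** Without clustering, the 95% half-width is 1.96 × 0.0867 = 0.17 points.
- An observed excess above 0.17 points gives P < 0.05 for harm.
- An observed excess below 0.5 − 0.17 = 0.33 points keeps the upper limit under the margin.
- Between 0.17 and 0.33 points both are true, and the two criteria point in opposite directions.

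This overlap needs a half-width below 0.25 points, that is, a design effect below (0.25/0.17)² ≈ 2.2. With more clustering the conflict takes another form. At an assumed design effect of 4, the half-width is 2 × 0.17 = 0.34 points, so an excess of 0.16 to 0.34 points is non-significant and also fails the margin. At that design effect, a true excess equal to the margin gives P > 0.05 in Φ(1.96 − 0.5/0.1733) ≈ 18% of trials.

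**5. Interval level alone.** Without clustering, the largest excess that passes is 0.5 − 1.96 × 0.0867 = 0.33 points at one-sided 2.5% and 0.5 − 1.645 × 0.0867 = 0.36 points at one-sided 5%. At a true effect of 0, this choice changes the verdict in about 0.005% of trials. It is a minor part of the problem.

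**The case against.** The strongest reply is that the plan should be read as one document. The margin, endpoint, population and model are all prespecified, and a competent analyst would set a confidence interval against 0.5%. A logistic model can also yield a standardised risk difference, so the model itself is not wrong. An odds-scale margin of 1.178 would be powered above 99.9% too, without clustering: SE of the log OR = sqrt(2 / (75,000 × 0.029 × 0.971)) = 0.0308, and Φ(0.164/0.0308 − 1.96) exceeds 0.999. All of this stands. It shows that the gap is easy to close, but not that the SAP closes it: scale, interval and rule remain unstated.

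Some stronger readings are tempting but unsupported:
- A reader might infer that the SAP prescribes an odds ratio and a test of no difference. It names neither. The odds scale follows from the model, and P < 0.05 is a general rule that does not expressly exclude a non-inferiority P value.
- The phrase about an effect of 0 does not by itself settle the scale, because zero is also the null on the log-odds scale. The absolute reading rests on the power check and the matching 0.6%.
- Using the same analysis for 2-day and 7-day mortality, which have no margin, most naturally means the same regression. It does not prove that a margin step was left out.
- The planned subgroup forest plot would ordinarily show effect intervals, although the SAP names none there and sets no margin rule.

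**Conclusion.** The point holds. The SAP sets and powers a 0.5-point absolute margin, then describes a primary analysis that never uses it, so the main hypothesis is not tested as written. This must be fixed. With 75,000 per arm, 2.9% mortality and no clustering, observed excesses of 0.17 to 0.33 points would be significant harm under the only stated criterion and yet non-inferior. The corresponding odds ratio runs from 1.14 to 1.21 across the printed hospital rates. With clustering these bounds shift, and the SAP gives no figure from which to say by how much.

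The finding does not mean that the sample size statement is wrong; it reproduces. A reader might also infer that the lack of a few-cluster correction (jackknife, t reference, choice of degrees of freedom) is part of this error. With eight hospitals that is a reasonable topic, but it is a separate and optional choice.

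**What to change.** In Primary outcome analysis, state that:
- non-inferiority is concluded if the upper limit of the two-sided 95% confidence interval for the adjusted risk difference (I-EWS minus EWS) in 30-day mortality is below 0.5 percentage points;
- the risk difference is obtained by standardisation from the planned logistic model, with a named standard-error method that accounts for clustering;
- the odds ratio is supportive, and P < 0.05 applies only to superiority comparisons;
- the per-protocol analysis remains a sensitivity analysis, with its interval shown against the same margin.

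The cost is one or two sentences and some code. Covariates, data and sample size do not change. The one added obligation is to choose the standard-error method before outcome data are seen.

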- 1. ≥18 years at admittance at participating hospital
- 2. Admittance in a department/Ward using systematised EWS
- 3. Admittance for more than 24 hours

Patients will be included at the first admission in the study period (index admission) and will remain in this group (intervention/control) for a follow-up period of 30 days. All subsequent admissions (readmissions) will be ignored.

Exclusion

- 1. Patients arriving at the gynaecological-, obstetric-, and paediatric department
- 2. If a "do not resuscitate"-order or "no NEWS/I-EWS registration" are identified, patients will be excluded for further analysis at the time of registration.

Definition of clusters

Eligible hospitals can consist of one or two units. A hospital is defined based on its administrative organisation and catchment area. Each hospital will generate one cluster and two (time) periods (control and intervention). See schematic figure 1 below

Randomisation

Prior to the study start participating clusters will be randomised to start as either intervention or control. Eight cluster will be available, and we will be using stratified randomisation based on size of hospitals (number of unique admissions, more than 25,000 admissions is defined as large hospitals, less than 25,000 is small hospitals), to balance a potential size difference between the intervention and control group. The randomization will be performed using computer-generated numbers. The randomisation will allocate participating hospitals to periods of intervention or control in a 1:1 ration. A cross-over will occur after 6.5 months and is expected to be at April 15, 2019.

Ethics

The study was presented to the Regional Ethics Committee, who decided that no formal approval was needed in accordance with Danish law (J.nr. 1701733). Data management has been approved by the Danish Data Protection Agency (ID: HGH-2017-116, I-suite:06030).

Study variables:

The following data are collected as a minimum for the included patients:

- Age and gender
- Personal Identification number (Danish Civil Registration number (CPR)

- Presence of Do Not Resuscitate (DNR) order
- Presence of "No EWS registration"
- EWS/I-EWS Scores
- Registered actions to the EWS/I-EWS escalation protocol
 - Responsible nurse contacted
 - Treatment plan already made
 - Doctor contacted
 - MET contacted
 - Other
 - Charlson Comorbidity Index

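### The primary mortality model has no period term, although each hospital's two periods are winter and summer and the plan itself assumes 25% variation in mortality over the year

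*SAP*

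**What the plan says.** The section on the primary outcome analysis says that the mortality comparison "will be done using logistic regression that accounts for clustering with adjustment for hospital ID, age, and sex". These are the only covariates. It does not say how clustering is to be taken into account (random effect, GEE or robust variance). The 2- and 7-day mortality analyses repeat this model, length of stay follows the same adjustment principles, and scores per patient per day are compared by linear regression with no covariates named. The sensitivity analyses add no calendar-time term.

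On timing, enrolment opens on 15 October 2018 and inclusion ends on 1 October 2019. On the switch, the Randomisation section says "A cross-over will occur after 6.5 months and is expected to be at April 15, 2019". Patients admitted in the 14-day implementation window and the 30-day observation window are left out.

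The sample size section lists as an assumption "a variation in mortality of 25% over the course of the year" and then states: "The non-inferiority margin is set at 0.5%, and if the intervention has an effect of 0, the study has above 90% power to confirm noninferiority". It does not say how the seasonal assumption enters the power calculation or the analysis.

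Only the first admission in the whole study counts: "All subsequent admissions (readmissions) will be ignored".

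**The concern.** After the excluded windows are removed, each hospital has one block from about 15 October to 15 March and one from about 29 April to 1 October. One is under I-EWS and the other under EWS, so within a hospital the treatment contrast is also the winter–summer contrast. Across hospitals, season cancels only if the two sequences carry equal weight, and eight hospitals of very unequal size cannot ensure that.

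Leaving period out then has one of two consequences, depending on the variance method:

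- **Patient-level (model-based) standard errors.** The estimate keeps a residual seasonal bias that the standard error ignores, so the non-inferiority test exceeds its nominal error rate.
- **Hospital-robust standard errors.** Hospitals in opposite sequences show seasonal effects of opposite sign. The variance estimator reads this as between-hospital noise, and power is lost.

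The first-admission rule adds a further difference between periods. Patients indexed in period 1 cannot enter period 2, so frequently admitted patients are depleted there. The document gives no figures to size this.

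At stake is the confirmatory safety conclusion on 30-day mortality.

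**Working it through.** **Inputs.** From the sample size section: 150,000 patients (taken as 75,000 per condition), mortality 2.9%, margin 0.5 points, true effect 0. From the hospital table: the eight admission counts, whose rows add to 189,905, and the deaths. From the Randomisation section: 1:1 allocation stratified at 25,000 admissions, which gives four large and four small hospitals. Assumed: one-sided alpha 0.025, equal period sizes, an exact 2:2 split within each stratum, and a test on the risk-difference scale, because the margin is absolute.

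**1. The plan's own figure.** SE = √(2 × 0.029 × 0.971 / 75,000) = 0.087 points. Power = Φ(0.5/0.087 − 1.96), about 99.99%. Power of 90% needs 23,671 per condition, so the claim holds as a bound, with room for a design effect of 75,000/23,671 = 3.17.

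**2. Size of the season effect (δ).** The plan does not define the 25%. Possible readings are:

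- Smooth curve with 25% peak-to-trough: the half-year means are 1 ± 0.125 × 2/π = 1 ± 0.080, a contrast of 16%, and δ = 0.159 × 2.9 = 0.46 points. With the actual windows the contrast is 14–18%.
- Winter/summer ratio of 1.25: δ = 3.22 − 2.58 = 0.64 points.
- Half-year means 25% apart: δ = 0.25 × 2.9 = 0.73 points.
- Plus or minus 25% between periods: δ = 3.63 − 2.18 = 1.45 points.

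**3. Sequence imbalance (D).** There are 6 × 6 = 36 stratified allocations. D is the patient share of one sequence minus that of the other. The worst case puts Herlev & Gentofte, Nordsjælland, Holbæk and Slagelse in one sequence:

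D = [(75,579 − 60,591) + (34,124 − 19,611)] / 189,905 = 29,501/189,905 = 15.5%.

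Over all 36, the mean of |D| is 6.8% and the RMS is 8.3%.

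**4. Patient-level SE, no period term.** Bias is about D × δ. False non-inferiority at the margin is Φ(−1.96 + bias/SE) when the bias favours I-EWS. For δ = 0.46 the worst bias is 0.155 × 0.46 = 0.07 points, and Φ(−1.96 + 0.07/0.087) is about 13%.

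**5. Hospital-robust SE, no period term.** With w the hospital shares, Σw² = 0.154, so season adds about √0.154 × δ = 0.39δ to the SE. For δ = 0.46: √((0.39 × 0.46)² + 0.087²) = 0.20 points. The estimate must then fall below 0.5 − 1.96 × 0.20 = 0.11, or below 0.5 − 2.365 × 0.20 = 0.03 with a t reference on 7 df. The estimate itself varies with SD √(0.087² + (0.083 × 0.46)²) = 0.095. Power is therefore roughly Φ(0.11/0.095), about 87%, or Φ(0.03/0.095), about 61%. Simulation agrees.

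**6. Results.** Worst bias and false non-inferiority use the patient-level SE. Power is for a true effect of 0 with the hospital-robust SE. CR1 is the usual small-sample factor. Ranges cover the risk-difference and logistic versions that were run.

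| δ (points) | Worst bias | False NI, mean / worst | Power without period: uncorrected z / CR1 z / CR1 t | Power with period |
|---|---|---|---|---|
| 0.46 | 0.07 | 4% / 12–14% | 86–88% / 79–83% / 55–59% | about 99% or more |
| 0.64 | 0.10 | 5% / 21% | 52% / 42% / 16% | about 99% or more |
| 0.73 | 0.11–0.12 | 6% / 24–27% | 32–33% / 23% / 6% | about 99% or more |
| 1.45 | 0.23 | 15% / 75% | 0% / 0% / 0% | 97% or more |

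With no season effect, the robust analysis without a period term has 99.8% power. The loss in the table therefore comes from the unmodelled period.

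**The case against.** **The design already does most of the work.** Every hospital has both conditions, and stratified randomisation puts both conditions in both seasons. Before allocation the expected bias is zero, and in about half of the allocations the bias works against I-EWS. At δ = 0.46 the average bias is 0.068 × 0.46 = 0.03 points, about 6% of the margin. This stands: the bias is partial, and 0.11 points needs both the worst allocation and a large contrast. The average error rate still exceeds 2.5%, however, and cancellation in the estimate does nothing for the robust standard error.

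**The two harms exclude each other.** With patient-level standard errors, average power stays at or above 98.7%. With robust ones, false non-inferiority at the margin is close to zero, so the test is conservative. This also stands, and the two should not be added together. But the plan does not say which method applies, and either one damages the primary test.

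**The largest losses rest on upper readings of the 25%.** This is fair: the 16% contrast is the better central case. At 14%, an uncorrected robust z-interval gives about 92% power. That interval is anti-conservative with eight clusters, and at 16% every robust variant falls below 90%.

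**The stated power may already allow for season.** The calculation is not shown, so this cannot be excluded, and the design-effect room of 3.17 is real. With a robust analysis it is not enough: an SE of 0.20 against 0.087 is a variance ratio of about 5.3.

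**The simulations leave out age and sex.** Adjusting for them could absorb part of a winter excess due to older case mix. How much is unknown.

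**Conclusion.** The concern holds. The plan recognises season when it sets the sample size and then leaves it out of the model, in a design where each hospital's treatment contrast is also a seasonal contrast. With a 16% winter–summer contrast, patient-level standard errors raise the average false non-inferiority rate from 2.5% to about 4% (12–14% in the worst allocation). Hospital-robust standard errors cut power from about 99% or more to 55–88%, depending on the correction and reference distribution. With a 25% contrast the figures are 6% on average (24–27% worst) and 6–33%.

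That the term is missing is certain. The size of the harm is less so. It depends on what the 25% means, on the unspecified clustering method, on the realised allocation (not given in the document), and on the assumptions of equal period sizes, one-sided 0.025 and a risk-difference test. The shift in case mix from the first-admission rule comes on top and is not quantified.

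**What to change.** Add a fixed effect for period (first or second block) to the primary logistic model. Add the same term to the 2- and 7-day mortality, length-of-stay and scores-per-day models. Calendar month within period could be added as a refinement.

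In the same edit, name the method for clustering and a small-sample correction suited to eight hospitals, and restate the power on that model. The period term alone does not settle this. With it in place and CR1 with a t reference, simulated false non-inferiority was still 2.5–3.8%. With patient-level standard errors and an assumed random hospital-by-period SD of 0.1 points it was about 5–7%. Also state what the 25% variation refers to.

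The cost is SAP wording and one covariate derived from the admission date, which is already collected. It uses one degree of freedom at cluster level. If there were no season effect, robust power would be essentially unchanged (99.8% in the simulation with or without the term). The change should be dated before outcome data are seen.
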